6.7. Dose Interruption and Reduction

The following are the guidelines for dose interruption and/or reduction. If an AE is attributed to study drug, the investigator's discretion will be used to determine if the drug not attributed to the AE will be withheld based on the investigator's assessment of risk-benefit of withholding the study drug.

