6.7.1. GS-5829

For subjects without lymphoma, if at any time in the study a subject experiences a toxicity consistent with a Grade 4 DLT (see Section 3.2 for the definition of a DLT), GS-5829 treatment will be discontinued permanently, with the exception of Grade 4 neutropenia or thrombocytopenia. If a subject experiences Grade 4 neutropenia or thrombocytopenia or any other < Grade 4 toxicity consistent with a DLT (per Section 3.2), dosing with GS-5829 will be postponed until the toxicity is resolved to Grade 0 or 1 (as defined by the CTCAE, version 4.03) or returns to the subject's baseline value. If the toxicity resolves to Grade 0 or 1 or returns to the subject's baseline value within 28 days from the start of the event, the subject may resume dosing of GS-5829 at a dose that is at least one dose level lower after discussion with the Gilead Medical Monitor.

For subjects with lymphoma, if the toxicity is neutropenia or thrombocytopenia consistent with the definition of a DLT, the dose may be resumed at either one lower dose level, or the same dose with an alternative dosing schedule, which decreases the total amount of GS-5829 administered over a 28 day period to at least 25% less than the previous cohort (eg 14 days on and 7 days off). If the subject experiences a recurrence of a non-hematologic toxicity meeting criteria for DLT after restarting study drug at a lower dose or if the toxicity does not resolve within 28 days, treatment with GS-5829 will be discontinued. For subjects with lymphoma, if the recurrent toxicity is hematologic a second dose decrease is allowed (lowest dose allowed 1.0 mg) in either total daily dose or by a change in schedule such that the total amount of GS-5829 administered over a 28 day period is decreased by at least 25% after discussion with the Gilead Medical Monitor.

Table 6-2. Dose Reduction of GS-5829

NCI CTCAE Grade	Recommendation	
	Group 1 and 2: Non-lymphoma GS-5829	Group 3: Lymphoma GS-5829
HEMATOLOGICAL ADVERSE EVENTS		
Neutropenia		
Grade ≤ 3 Neutropenia	Maintain current dose level and schedule.	

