Grade 4 neutropenia (or occurrence of Grade ≥ 3 neutropenia (ANC < 1000/mm ³) with fever (a single temperature of > 38.3°C or a sustained temperature of ≥ 38°C for more than one hour) or infection	Hold dosing with GS-5829 until the toxicity is resolved to ≤ 1. If the toxicity resolves to ≤ 1 within 28 days, the subject may resume dosing of GS-5829 at a dose that is at least one dose level lower after discussion with the Gilead Medical Monitor. Granulocyte-colony Stimulating Factor (GCSF) is allowed	Hold dosing with GS-5829 until the toxicity is resolved to ≤ 1. If the toxicity resolves to ≤ 1 within 4 days, the subject may resume dosing of GS-5829 at the same dose or a dose lower. If recovery to grade ≤ 1 takes > 4 days, but within 28 days, then the subject may resume dosing of GS-5829 at a dose that is at least one dose level lower after discussion with the Gilead Medical Monitor. GCSF is allowed during dose interruption, but is not to be administered on the same day as GS-5829
Thrombocytopenia		
Grade ≤ 2 Thrombocytopenia	Maintain current dose level and schedule.	
Grade 3 Thrombocytopenia	Hold dosing with GS-5829 until the toxicity is resolved to ≤ 1. If the toxicity resolves to ≤ 1 within 28 days, the subject may resume dosing of GS-5829 at a dose that is at least one dose level lower after discussion with the Gilead Medical Monitor	Hold dosing with GS-5829 until the toxicity is resolved to ≤ 1. If the toxicity resolves within 7 days, the subject may either resume at the same dose or a dose with is one level lower or at an intermittent dosing schedule. If the toxicity takes > 7 days to resolve to ≤ Grade 1, then the drug must be resumed at a lower dose or an intermittent dosing schedule after discussion with the Gilead Medical Monitor
Grade 4 Thrombocytopenia	Hold dosing with GS-5829 until the toxicity is resolved to ≤ 1. If the toxicity resolves to ≤ 1 within 28 days, the subject may resume dosing of GS-5829 at a dose that is at least one dose level lower after discussion with the Gilead Medical Monitor. If it takes > 28 days, then GS-5829 will be permanently discontinued	Hold dosing with GS-5829 until the toxicity is resolved to ≤ 1 at which time the subject may either resume at a dose with is one level lower, or at intermittent dosing schedule (at least 25% less GS-5829 in a 28 day dosing period) after discussion with the Gilead Medical Monitor.

NCI CTCAE Grade	Recommendation	

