	Group 1 and 2: Non-lymphoma GS-5829	Group 3: Lymphoma GS-5829
NON-HEMATOLOGICAL ADVERSE EVENTS		
Hepatic Adverse Events (elevations in ALT, AST or bilirubin)		
Grade 1 (ALT/AST \leq 3xULN) (Bilirubin \leq 1.5xULN)	Maintain current dose level and schedule.	
Grade 2 (ALT/AST > 3-5xULN) (Bilirubin > 1.5 - \leq 3xULN)	Maintain current dose level and schedule. Monitor ALT, AST, ALP, and bilirubin at least 1x per week.	
Grade 3	Hold dosing until \leq grade 2. Permanently discontinue if any Grade 3 or Grade 4 elevation in AST or ALT associated with a Grade 2 elevation in bilirubin	
Grade 4	Permanently discontinue GS-5829	
Non hepatic, non-hematologic adverse events		
Grade \leq 2	No change in dosing required. Dosing may be interrupted until Grade \leq 1 or baseline	
Grade 3	Hold dosing until \leq grade 1 and decrease dose by at least one dose level and or by a change in schedule which decreases total GS-5829 administered over a 28 day dosing period	
Grade 4	Permanently discontinue GS-5829	

If the subject was not receiving GS-5829 at the time disease progression was documented (eg, due to reversible toxicity), after discussion with the Gilead Sciences Medical Monitor, GS-5829 may be re-started if the criteria for resuming treatment as described in Section 6.7.1 are met and the Investigator feels it is in the subject's best interest to do so.

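### For subjects without lymphoma, the non-hematologic rows of Table 6-2 are more permissive than the Section 6.7.1 text for DLT-type toxicities below Grade 4, and no sentence says which governs

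*Protocol*

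**What the plan says.** Protocol Section 6.7 introduces the dose-modification rules with "The following are the guidelines for dose interruption and/or reduction". Section 6.7.1 then sets out text and Table 6-2.

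The text for subjects without lymphoma applies at any time in the study. Apart from Grade 4 neutropenia and thrombocytopenia, it covers "any other < Grade 4 toxicity consistent with a DLT (per Section 3.2"). For these, "dosing with GS-5829 will be postponed until the toxicity is resolved to Grade 0 or 1" or to the subject's baseline. If that happens within 28 days of onset, "the subject may resume dosing of GS-5829 at a dose that is at least one dose level lower after discussion" with the Medical Monitor.

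Table 6-2 sorts events by type and CTCAE grade under the heading Recommendation. For non-hepatic, non-hematologic events of Grade 2 or lower it says "No change in dosing required. Dosing may be interrupted until Grade" 1 or lower, or baseline. Grade 2 hepatic events keep dose and schedule, with weekly monitoring. Grade 3 hepatic events are held only to Grade 2 or lower, with one exception: "Permanently discontinue if any Grade 3 or Grade 4 elevation in AST or ALT associated with a Grade 2 elevation in bilirubin". Grade 3 non-hepatic events are held to Grade 1 or lower, then restarted at a lower level and/or on a reduced schedule.

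Protocol Section 3.2 (Groups 1 and 2) counts as DLTs, if possibly related: bleeding of Grade 2 or higher; a non-hematologic event of Grade 2 or higher that the investigator judges significant enough to make further escalation an unacceptable risk; most non-hematologic toxicity of Grade 3 or higher; and an interruption of 7 days or more for unresolved toxicity. Laboratory findings without a clear clinical correlate may go to discussion with the Medical Monitor.

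**The concern.** The same event can draw two different instructions from one section. A site that consults only the table row could keep a subject on full dose after a related Grade 2 bleed, although Section 3.2 makes that a DLT and the text requires a hold and then a lower dose.

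Bleeding is a named risk in this study. Section 5.4 reports bleeding in dogs by an unexplained mechanism and prohibits anticoagulants. Section 1.5 reports an adrenal hemorrhage DLT at 4 mg (grade not stated) in a subject with normal coagulation parameters and a platelet count above normal. What is at stake is subject safety and uniform dosing across sites, not an error rate or a sample size.

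**Working it through.** The plan gives no figure to reproduce. The check is a comparison of rules, followed by simple arithmetic on the dose ladders.

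**Step 1. Text against table, non-lymphoma, below Grade 4, event consistent with a DLT.** In every row the text requires a hold to Grade 0–1 or baseline and, if resolved within 28 days, allows restart at least one level lower after Medical Monitor discussion.

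| Event | Table 6-2 | Table relative to text |
|---|---|---|
| (i) Grade 2 non-hepatic DLT, most naturally including bleeding | No change required; hold optional; no reduction, 28-day limit or discussion stated | More permissive |
| (ii) Grade 2 hepatic event judged a DLT | Dose and schedule maintained | More permissive |
| (iii) Grade 3 ALT/AST assessed as a DLT, no Grade 2 bilirubin | Hold to Grade 2 or lower; no reduction or 28-day limit stated | More permissive |
| (iv) Grade 3 non-hepatic DLT | Hold to Grade 1 or lower; schedule change allowed in place of a lower level; no 28-day limit stated | More permissive on restart |
| (v) Grade 3 AST/ALT with Grade 2 bilirubin | Permanent discontinuation | Stricter |

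Within (i), if the event is a DLT only because dosing was interrupted for 7 days or more, the hold has already happened. The difference is then the missing step-down, 28-day limit and discussion.

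**Step 2. Do the other rows agree with the text?** For Grade 4 neutropenia and for Grade 3 and Grade 4 thrombocytopenia, the Groups 1 and 2 column repeats it: "Hold dosing with GS-5829 until the toxicity is resolved to ≤ 1", then 28 days, one level lower, Medical Monitor. The table also lifts febrile Grade 3 neutropenia, a DLT, out of its permissive row for neutropenia of Grade 3 or lower. The Grade 2 non-hepatic row has no such carve-out. This pattern suggests a drafting gap rather than an intended exception.

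**Step 3. Size of one step down.** Nominal reduction = 1 − lower level / current level, from Tables 3-1 and 3-2.

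- Group 1: 1.4→0.6 mg, 57.1%; 2→1.4, 30.0%; 3→2, 33.3%; 4→3, 25.0%; 6→4, 33.3%; 9→6, 33.3%; 12→9, 25.0%.
- Group 2: 3→2 mg, 33.3%; 4→3, 25.0%; 6→4, 33.3%; 9→6, 33.3%; 12→9, 25.0%.
- At 4 mg over 28 days of dosing: 4 × 28 = 112 mg under row (i); at most 3 × 28 = 84 mg under the text.

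**Step 4. ALT/AST level at restart, row (iii).** By the grade limits printed in Table 6-2, Grade 1 ends at 3 × ULN and Grade 2 at 5 × ULN. The ceiling is therefore 3 × ULN under the text and 5 × ULN under the table. The two can coincide through the text's baseline clause for subjects with liver metastases, who may enter at up to 5 × ULN (Section 4.2).

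**Step 5. Precedence.** Neither document ranks text over table. A blanket rule either way would not be the safer one throughout: the text is stricter in (i) to (iv), the table in (v).

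**The case against.** The best defence is that the two can be read together. The text is specific to DLT-type toxicity and mandatory. The table is a general guide by grade, headed as a recommendation, and a row that requires no change does not forbid a hold. A site that follows the stricter instruction satisfies both. In its laboratory-findings clause, Section 3.2 itself links a DLT to dose reduction. Section 7.5 has treatment-emergent toxicities brought to the Medical Monitor's attention whatever the table row says, and sends questions there too. For a Grade 2 event that is a DLT by investigator judgement, the investigator has already found the risk of further escalation unacceptable and is unlikely to fall back on the routine row. For isolated laboratory findings that go to discussion, the Medical Monitor is already involved.

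Much of this stands. It makes unnoticed full-dose continuation less likely, and it shows that the conflict can be resolved. It does not correct the permissive rows, because Section 7.5 does not say which rule applies and no sentence makes the text override the table.

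A reader might infer that the protocol directs sites to continue full dose after a Grade 2 bleed. It does not: the row makes a hold optional, and the text above it makes the hold compulsory. A reader might also infer that DLT counts or the MTD are distorted. They are not, since both rest on Section 3.2 and the escalation rules, which this conflict leaves alone.

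**Conclusion.** The inconsistency is real and worth correcting. It covers four kinds of event below Grade 4 in subjects without lymphoma, with a fifth where the table is the stricter. Under row (i) the difference is full dose against at least one level lower, nominally 25.0% to 57.1%. Under row (iii) it is a restart ceiling of 5 rather than 3 × ULN, plus the missing step-down. These are ratios from the dose tables and grade limits, not exposures or risks, and the documents give no frequency for the events.

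Row (i) assumes that bleeding belongs with non-hepatic, non-hematologic events. No sentence says so. If it does not belong there, Table 6-2 has no row for bleeding, and the conflict remains for other Grade 2 DLTs. Sites in France enroll only Group 3, so the mismatch concerns the approximately 5 US centers. DLT classification, MTD rules and the planned analyses are unaffected. The SAP records the study as completed with 33 subjects, so the point concerns the plan as written; nothing in the documents shows that a subject was dosed wrongly because of it.

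**What to change.** Add one sentence to Section 6.7.1 and a matching footnote to the non-hematologic rows of Table 6-2, both limited to subjects without lymphoma:

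> For any toxicity below Grade 4 consistent with a DLT per Section 3.2 (including Grade 2 bleeding), the 6.7.1 text applies (hold to Grade 0–1 or baseline; if resolved within 28 days, may resume at least one dose level lower after Medical Monitor discussion) unless Table 6-2 is stricter, as for Grade 3 AST/ALT with Grade 2 bilirubin (permanent discontinuation).

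A single rule is better than editing individual cells. The non-hematologic rows give one instruction with no separate Group 3 entry, so unrestricted cell edits would also change Group 3 dosing. Editing only the Grade 2 row would leave Grade 3 bleeding handled more loosely than Grade 2 bleeding.

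The cost is protocol wording, with no added assessments. The downside is slightly more holds and reductions after Grade 2 DLTs, which the text already requires. The clinical content is for the sponsor's medical team to confirm.

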7. ADVERSE EVENTS AND TOXICITY MANAGEMENT

7.1. Definitions of Adverse Events, Adverse Reactions, and Serious Adverse Events

7.1.1. Adverse Events

An adverse event (AE) is any untoward medical occurrence in a clinical study subject administered a medicinal product, which does not necessarily have a causal relationship with the treatment. An AE can therefore be any unfavorable and/or unintended sign, symptom, or disease temporally associated with the use of a medicinal product, whether or not considered related to the medicinal product. AEs may also include pre- or post-treatment complications that occur as a result of protocol specified procedures, lack of efficacy, overdose, drug abuse/misuse reports, or occupational exposure. Preexisting events that increase in severity or change in nature during or as a consequence of participation in the clinical study will also be considered AEs.

An AE does not include the following:

- Medical or surgical procedures such as surgery, endoscopy, tooth extraction, and transfusion. The condition that led to the procedure may be an AE and must be reported.
- Pre-existing diseases, conditions, or laboratory abnormalities present or detected before the screening visit that do not worsen
- Situations where an untoward medical occurrence has not occurred (e.g., hospitalization for elective surgery, social and/or convenience admissions)
- Overdose without clinical sequelae (see Section 7.6.1)
- Any medical condition or clinically significant laboratory abnormality with an onset date before the consent form is signed and not related to a protocol-associated procedure is not an AE. It is considered to be pre-existing and should be documented on the medical history CRF.

7.1.2. Serious Adverse Events

A **serious adverse event** (SAE) or serious adverse drug reaction (SADR) is defined as an event that, at any dose, results in the following:

- Death
- Life-threatening (Note: The term “life-threatening” in the definition of “serious” refers to an event in which the subject was at risk of death at the time of the event; it does not refer to an event that hypothetically might have caused death if it were more severe.)
- In-patient hospitalization or prolongation of existing hospitalization

- Persistent or significant disability/incapacity
- A congenital anomaly/birth defect
- A medically important event or reaction: such events may not be immediately life-threatening or result in death or hospitalization but may jeopardize the subject or may require intervention to prevent one of the other outcomes constituting SAEs. Medical and scientific judgment must be exercised to determine whether such an event is a reportable under expedited reporting rules. Examples of medically important events include intensive treatment in an emergency room or at home for allergic bronchospasm; blood dyscrasias or convulsions that do not result in hospitalization; and development of drug dependency or drug abuse. For the avoidance of doubt, infections resulting from contaminated medicinal product will be considered a medically important event and subject to expedited reporting requirements.

Clarification of Serious Adverse Events

- Death is an outcome of an AE, and not an AE in itself
- An SAE may occur even if the subject was not on study drug at the time of occurrence of the event. Dosing may have been given as treatment cycles or interrupted temporarily before the onset of the SAE
- “Life-threatening” means that the subject was at immediate risk of death from the event as it occurred. This does not include an event that might have led to death if it had occurred with greater severity
- Complications that occur during hospitalizations are AEs. If a complication prolongs the hospitalization, it is a SAE
- “In-patient hospitalization” means the subject is formally admitted to a hospital for medical reasons, for any length of time. This may or may not be overnight. It does not include presentation and care within an emergency department
- The investigator should attempt to establish a diagnosis of the event on the basis of signs, symptoms and/or other clinical information. In such cases, the diagnosis should be documented as the AE and/or SAE and not the individual signs/symptoms

7.1.3. Clinical Laboratory Abnormalities and Other Abnormal Assessments as Adverse Events or Serious Adverse Events

Laboratory abnormalities without clinical significance are not recorded as AEs or SAEs. However, laboratory abnormalities (eg, clinical chemistry, hematology, and urinalysis) that require medical or surgical intervention or lead to study drug interruption, modification, or discontinuation must be recorded as an AE, as well as an SAE, if applicable. In addition, laboratory or other abnormal assessments (eg, ECG, x-rays, vital signs) that are associated with

signs and/or symptoms must be recorded as an AE or SAE if they meet the definition of an AE or SAE as described in Sections 7.1.1 and 7.1.2. If the laboratory abnormality is part of a syndrome, record the syndrome or diagnosis (eg, anemia), not the laboratory result (ie, decreased hemoglobin).

7.2. Assessment of Adverse Events and Serious Adverse Events

The investigator or qualified subinvestigator is responsible for assessing AEs and SAEs for causality and severity, and for final review and confirmation of accuracy of event information and assessments.

7.2.1. Assessment of Causality for Study Drugs and Procedures

The investigator or qualified subinvestigator is responsible for assessing the relationship to study drug therapy using clinical judgment and the following considerations:

- **No:** Evidence exists that the AE has an etiology other than the study drug. For SAEs, an alternative causality must be provided (eg, pre-existing condition, underlying disease, intercurrent illness, or concomitant medication).
- **Yes:** There is reasonable possibility that the event may have been caused by the study drug.

It should be emphasized that ineffective treatment should not be considered as causally related in the context of AE reporting.

The relationship to study procedures (eg, invasive procedures such as venipuncture or biopsy) should be assessed using the following considerations:

- **No:** Evidence exists that the AE has an etiology other than the study procedure.
- **Yes:** The AE occurred as a result of protocol procedures, (eg, venipuncture)

7.2.2. Assessment of Severity

The severity of AEs will be graded using the CTCAE, Version 4.03 ([Appendix 6](#)). For each episode, the highest severity grade attained should be reported.

If a CTCAE criterion does not exist, the investigator should use the grade or adjectives: Grade 1 (mild), Grade 2 (moderate), Grade 3 (severe), Grade 4 (life-threatening), or Grade 5 (fatal) to describe the maximum intensity of the AE. For purposes of consistency with the CTCAE, these intensity grades are defined in [Table 7-1](#).

Table 7-1. Grading of Adverse Event Severity

Grade	Adjective	Description
Grade 1	Mild	Sign or symptom is present, but it is easily tolerated, is not expected to have a clinically significant effect on the subject's overall health and well-being, does not interfere with the subject's usual function, and is not likely to require medical attention.
Grade 2	Moderate	Sign or symptom causes interference with usual activity or affect clinical status, and may require medical intervention.
Grade 3	Severe	Sign or symptom is incapacitating or significantly affects clinical status and likely requires medical intervention and/or close follow-up.
Grade 4	Life-threatening	Sign or symptom results in a potential threat to life.
Grade 5	Fatal	Sign or symptom results in death.

The distinction between the seriousness and the severity of an AE should be noted. Severe is a measure of intensity; thus, a severe reaction is not necessarily a serious reaction. For example, a headache may be severe in intensity, but would not be classified as serious unless it met 1 of the criteria for serious events listed in Section 7.1.2.

7.3. Investigator Requirements and Instructions for Reporting Adverse Events and Serious Adverse Events to Gilead

7.3.1. Requirements for Collection Prior to Study Drug Initiation:

After informed consent, but prior to initiation of study medication, the following types of events should be reported on the eCRF: all SAEs and AEs related to protocol-mandated procedures.

7.3.2. Adverse Events

Following initiation of study medication, collect all AEs, regardless of cause or relationship, until 30 days after last administration of study drug must be reported to the eCRF database as instructed.

All AEs should be followed up until resolution or until the AE is stable, if possible. Gilead Sciences may request that certain AEs be followed beyond the protocol defined follow up period.

